2.3.1 Known Potential Risks

All subjects:

- i) Risks associated with down-titration/discontinuation of beta-blocker: Adverse drug withdrawal events including tachycardia, worsened hypertension, palpitations, diaphoresis, shortness of breath, heart failure exacerbation, angina, myocardial infarction, cerebrovascular accident, arrhythmia, hospitalization, and death (shown to occur with abrupt cessation of beta-blocker)
- ii) Risks associated with beta-blocker use (and re-initiation/up-titration): Adverse drug events or adverse drug reactions including bradycardia, heart block, hypotension, dizziness, fatigue, depression, confusion, heart failure exacerbation, cerebrovascular accident, hospitalization, and death
- iii) Risks associated with wearing the Garmin wearable device: Local skin irritation, wrist pain
- iv) Risks associated with subject interviews: Emotional distress related to answering interview questions, and breach of confidentiality
- v) Risks associated with Cardiopulmonary Exercise Test and Short Physical Performance Battery: musculoskeletal injury, arrhythmias, acute coronary syndrome, hemodynamic instability, cardiovascular collapse, death.
- vi) Risks associated with Short physical performance battery: falling, musculoskeletal injury.
- vii) Risks associated with the 6-minute walk test: fatigue, dizziness.
- viii) Risks associated with blood draws: pain or bruising, dizziness, infection at the site of the blood draw

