2.3.3 Assessment of Potential Risks and Benefits

Rationale to exposing subjects to risk

- 1.) Exposure to beta-blocker: Subjects are already on beta-blocker at the time of recruitment; thus, being on beta-blocker does not explicitly add additional risk beyond usual clinical care
- 2.) Down-titration/discontinuation: Subjects will have their beta-blocker dose decreased and/or discontinued. There is limited data to support the benefits of beta-blocker in HFP EF, despite its frequent use. Moreover, beta-blocker use poses several harms in older adults including bradycardia, heart block, hypotension, dizziness, fatigue, depression, confusion, heart failure exacerbation, cerebrovascular accident, hospitalization and death. Accordingly, down-titration/discontinuation of beta-blocker may actually be safer than continuing beta-blocker, at least in some.

To mitigate the risks of down-titration/discontinuation, we will incorporate the following:

- 1.) remote monitoring protocol that includes assessments of resting heart rate and blood pressure
- 2.) telephone calls made by the research team to the subject on the day before a dose modification is planned, to instruct about the next day's dose change; the day a dose modification is planned, to confirm the dose change was made and the assess health status; and the day following dose modification, to reassess health status, where we will ascertain whether the subject is experiencing any withdrawal effects such as chest pain, tachycardia, palpitations, diaphoresis, and shortness of breath, as well as any adverse events, such as hospitalizations and/or adverse cardiovascular events, including HF exacerbation, myocardial infarction, arrhythmia, cerebrovascular accident and death; based off of subject feedback, telephone calls may be eliminated during the last 2 weeks of each period
- 3.) We will also provide a 24 hour/7 day per week hotline for subjects to call if they develop any concerning symptoms. Importantly, we will exclude subjects with other indications for beta-blocker use to maximize safety. For example, individuals with hypertrophic cardiomyopathy will be excluded, since beta-blockers have a clear benefit in this condition (and are a Class I indication).

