addition, they will undergo the short physical performance battery at baseline and at the end of each intervention period. The study team will discuss the components of the CPET with the subjects prior to their end of period visits.

Through a pre-existing remote monitoring program at Weill Cornell Medicine, we will provide subjects with a computer tablet and blood pressure cuff free-of-charge. This will allow us to collect vital sign data, including blood pressure and heart rate. We will encourage subjects to collect data up to 3 times per week. Based on patient reports of any concerning symptomatology, we may encourage increased frequency of assessments at different time points of the study. Also, based on prior experience, some subjects may want to collect data more frequently, which will allow. This approach was developed based on our preliminary data from 9 prior N-of-1 trials, where there were no serious adverse events and based on subject feedback (Several subjects requested reduced frequency of required vital sign assessment). If we encounter “Red Flags” (Table 3), we will call the subject to assess symptoms and determine the need for medical attention and/or study withdrawal.

Table 3. Red Flags triggering phone call

| | Upper Limit | Lower Limit |
|--------------------|--------------------|--------------------|
| Blood Pressure | >160/90 mmHg | <100/60 mmHg |
| Resting Heart Rate | >100 bpm | <60 bpm |

Remote monitoring will occur on a daily basis. Subjects will be provided with a tablet computer and blood pressure cuff free-of-charge. These data will be automatically uploaded to an online portal, which we will review weekly.

Subjects will complete subject-reported outcome questionnaires on quality of life, cognitive function, and sexual function at regular intervals set by each of the validated instruments during the intervention stage via their tablet computers, over the phone, or via email.

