6.1.2 Treatment Phase

6.1.2a Daily

- Remote Monitoring
 - Remote monitoring will collect vital sign data, including blood pressure and heart rate via a free of charge remote monitoring platform already in use in the HFpEF Program. Data will be reviewed weekly. If we encounter “Red Flags”, we will call the subject to assess symptoms, and determine the need for medical attention and/or study withdrawal in consultation with the subject’s other physicians and the DSMB.
 - Red Flags are as follows:
 - Blood pressure >160/90 mmHg or <100/60 mmHg
 - Heart Rate >100 bpm or <50 bpm
- Step Count
 - Daily step count will be collected via Garmin wearable devices that will be provided to subjects during the duration of the treatment phase of the trial.

6.1.2b Weekly

- Dose modification (as described in section 3.1)
- Telephone Contact on the day prior to the dose modification, the day of the dose modification and on the day following dose modification. Telephone calls may be eliminated during the last 2 weeks of each period per subject feedback.
- Patient Reported Outcomes (PROMIS-29, PROMIS-SF 6A) via web-based surveys taken at home on tablet computers provided to each subject, over the phone, or via email – frequency/length of surveys may be decreased per subject feedback
- Interim Events History (Adverse Events/SAE) will be asked during each phone call

6.1.2.c Biweekly

- Kansas City Cardiomyopathy Questionnaire (KCCQ-12)

6.1.2d End of Periods

- Medication Inventory
- Dose Modification
- Physical Exam, including vital signs
- Central blood pressure assessment via the UScom BP+ device, when possible
- Electrocardiogram
- Six Minute Walk Test
- Cardiopulmonary Exercise Test (at the end of Period 1 and Period 2)
 - We may draw additional blood for Troponin & NT-proBNP directly after the CPET. On visits which include a CPET, the subject may have Troponin and NT-proBNP drawn twice.
- Blood Draw for Troponin & NT-proBNP
- Blood draw for future research (at end of period 1 & end of period 2 only)
- Short Physical Performance Battery
- Qualitative interview on understandability and usability of study materials
- EQ-5D VAS
- PROMIS-29
- PROMIS-SF 6A
- PROMIS-Sexual Function

- Kansas City Cardiomyopathy Questionnaire (KCCQ-12)
- Interim Events History

6.1.2e End of Intervention Visit Period

- Medication Inventory
- Dose Modification
- Physical Exam
- Central blood pressure assessment via the UScom BP+ device
- Electrocardiogram
- Six Minute Walk Test

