7.4 Dosing and Administration

We have created a down-titration schedule, where we will reduce the dose of each beta-blocker by 50% every week, a schedule used in a prior deprescribing study of antihypertensives, that included beta-blockers. This schedule accounts for a sufficient number of half-lives to ensure drug clearance and accounts for changes in receptor density and related adrenergic hypersensitivity linked to withdrawal symptoms and ADWES observed after abrupt beta-blocker cessation. Re-initiation/up-titration will be done in reverse order. Subjects will never go on a dosage higher than their usual home dose. All drugs will be administered orally. To assist subjects with dose reduction, each subject will receive pill cutters.

| Table 4: Examples of drug down-titration schedule for selected β-blockers | | | | | |
|--|---------------|---------------|---------------|---------------|-----------------|
| Examples | Week 1 | Week 2 | Week 3 | Week 4 | Week 5+6 |
| Metoprolol 200mg daily | 100mg daily | 50mg daily | 25mg daily | 12.5mg daily | Off |
| Carvedilol 50mg BID | 25mg BID | 12.5mg BID | 6.25mg BID | 3.25mg BID | Off |
| Bisoprolol 10mg daily | 5mg daily | 2.5mg daily | Off | Off | Off |
| Atenolol 100mg daily | 50mg daily | 25mg daily | 12.5mg daily | Off | Off |
| Betaxolol 20mg daily | 10mg daily | 5mg daily | 2.5mg daily | Off | Off |
| Nebivolol 40mg daily | 20mg daily | 10mg daily | 5mg daily | Off | Off |
| Nadolol 320mg daily | 160mg daily | 80mg daily | 40mg daily | Off | Off |
| Propranolol 40mg BID | 20mg BID | 10mg BID | 5mg BID | Off | Off |
| Acetbutolol 600mg BID | 300mg BID | 150mg BID | 75mg BID | Off | Off |
| Penbutolol 80mg daily | 40mg daily | 20mg daily | 10mg daily | Off | Off |
| Pindolol 30mg BID | 15mg BID | 7.5mg BID | Off | Off | Off |
| Labetalol 1200mg BID | 600mg BID | 300mg BID | 150mg BID | Off | Off |

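### The low heart-rate limit that triggers a safety call is <60 bpm in Table 3 but <50 bpm in section 6.1.2a, and nothing says which governs

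*Combined protocol and SAP*

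**What the plan says.** Section 3.1 has a table headed "Table 3. Red Flags triggering phone call". Its heart-rate row is "Resting Heart Rate | >100 bpm | <60 bpm". Section 6.1.2a, which sets out the daily procedures of the treatment phase, gives its own list without referring to Table 3. There the heart-rate entry is "Heart Rate >100 bpm or <50 bpm" and the blood-pressure entry is "Blood pressure >160/90 mmHg or <100/60 mmHg". The prescribed response in 6.1.2a is that "we will call the subject to assess symptoms, and determine the need for medical attention and/or study withdrawal". Section 3.1 prescribes the same call; 6.1.2a adds consultation with the subject's other physicians and the DSMB.

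Section 2.3.1 lists "Risks associated with beta-blocker use (and re-initiation/up-titration): Adverse drug events or adverse drug reactions including bradycardia" among the known risks. Section 7.4 limits exposure: "Subjects will never go on a dosage higher than their usual home dose".

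On the secondary point, section 2.3.3 includes among its risk mitigations "telephone calls made by the research team to the subject on the day before a dose modification is planned", with further calls on the day of the change and the day after. Sections 2.3.3, 4.6, 6.1 (footnote 6), 6.1.2b and 7.9 each allow calls to be dropped in the final two weeks of a period. None of the five makes an exception for a dose change.

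**The concern.** A safety trigger should have one value. Here a reading of, say, 55 bpm requires a call under one section and none under another, and both are current text. Two staff members could handle the same reading differently, and a monitor would have no single standard against which to check adherence.

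The low limit matters because the protocol has few other numeric safeguards against a slow heart rate. Exclusion criterion 2g sets upper rate limits only. The withdrawal criteria in 8.2 give no heart rate, and the table of actions in 13.4 has no row for bradycardia. End-of-period visits may be remote, without physical assessment or EKG, so remote readings may be the only heart-rate data the protocol collects in that period. Subjects are 65 or older and may be returned to full home dose more than once.

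The late-call option raises a related but smaller question: whether calls that serve as a mitigation for dose changes can be dropped at a dose change.

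**Working it through.** **Heart-rate limit.** No plan figure has to be reproduced. The check compares the two lists.

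| Limit | 3.1, Table 3 | 6.1.2a | Agree? |
|---|---|---|---|
| Heart rate, upper | >100 bpm | >100 bpm | Yes |
| Blood pressure, upper | >160/90 mmHg | >160/90 mmHg | Yes |
| Blood pressure, lower | <100/60 mmHg | <100/60 mmHg | Yes |
| Heart rate, lower | <60 bpm | <50 bpm | **No** |

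1. The limits differ by 60 − 50 = 10 bpm. In whole beats, Table 3 flags 59 and below and 6.1.2a flags 49 and below, so they disagree on 50 to 59 bpm.
2. Table 3 says resting heart rate and 6.1.2a says heart rate. This does not reconcile them: 2.3.3 describes the remote monitoring as assessing resting heart rate, and both lists apply to those readings and trigger the same call.
3. The rest of the protocol contains no third value and no rule of precedence. Neither statement is in an amendment log.
4. No mean or SD for heart rate is given, so the share of readings in the disputed band is not estimated.

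**Late calls (secondary).** Inputs: weekly steps and example schedules from Table 4; re-initiation in reverse order (7.4); six-week periods. Assumption, from Table 4's weekly columns: each step falls on day 1 of its week.

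1. First Off week in the 12 example rows of Table 4: week 5 in 2 (metoprolol 200 mg daily, carvedilol 50 mg BID), week 4 in 8, week 3 in 2.
2. For the two longest schedules the week-5 step falls on day 4 × 7 + 1 = 29. Its calls fall on days 28, 29 and 30.
3. The last two weeks of a 42-day period are days 29 to 42, so 2 of the 3 calls may be dropped. The day-before call is in week 4 and is unaffected.
4. Going down, this is the step to Off. Going up, it is the step to full home dose: metoprolol 100 to 200 mg daily, carvedilol 25 to 50 mg BID.
5. Period 1 of an A-first sequence stays at home dose, so it has no titration. Droppable calls = 2 × titration periods:

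| Sequence | Titration periods | Droppable calls |
|---|---|---|
| AB | 1 | 2 |
| BA | 2 | 4 |
| ABAB | 3 | 6 |
| BABA | 4 | 8 |
| ABABAB | 5 | 10 |
| BABABA | 6 | 12 |

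These are ceilings for a subject on a five-step schedule with every optional call dropped. Table 4 gives examples and not the mix of subjects, so the number affected is unknown and could be zero.

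**The case against.** The mismatch itself is hard to dispute; the case on the other side is about how much it matters. The two texts do not impose incompatible duties, since calling below 60 bpm meets both. The flag is not a stopping or dosing rule, and vitals are reviewed only weekly, so neither limit is a rapid alarm. Subjects already take the drug, never exceed their home dose, and may enrol with a resting rate of 50 to 59 bpm because eligibility sets no lower limit. The limits most relevant to withdrawal of the drug, which is the main added exposure, agree in both places. Calls around dose changes, the 24-hour hotline, event history and, at in-person visits, examination and EKG offer other routes to detection. No analysis uses the flag.

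All of this stands as a limit on the consequence. It does not remove the defect. Nothing tells staff to apply the stricter list, and someone following 6.1.2a as written would leave out contact that Table 3 requires. Up-titration is a study procedure with bradycardia as a named risk.

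On late calls, the objection is that dropping them is optional, generally tied to subject feedback, and a deliberate way to reduce burden in a feasibility study. The weekly questionnaire contact, end-of-period event history and hotline would remain. That is fair and is why the point is secondary.

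**Conclusion.** The concern holds. This is an internal inconsistency in a safety threshold: two current values, 10 bpm apart, for the same readings and the same action, with no precedence stated. It should be corrected because one version omits safety calls that the other requires. That conclusion rests on the text alone and on no assumption about how often readings fall at 50 to 59 bpm, which the documents do not allow one to estimate. They also do not show which value was intended. The power statement and the planned On versus Off comparisons are unaffected.

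The late-call gap is real for five-step schedules, given a six-week period and a step on day 29, but it carries none of the weight of this conclusion.

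**What to change.** Put one low heart-rate limit, agreed with the DSMB, in both Table 3 and 6.1.2a, or have 6.1.2a refer to Table 3 so that the value is stated once. A limit of <60 bpm is the more cautious and satisfies both current texts. The change is one number in one place. Choosing <60 rather than <50 bpm means more red-flag calls in On periods; the documents do not allow a count.

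Secondary: in 2.3.3, 4.6, 6.1 footnote 6, 6.1.2b and 7.9, exempt the calls on the day before, the day of and the day after any dose change from the option to drop late-period calls. This is one short exception in five places. It keeps at most 2 calls per titration period for a subject on a five-step schedule, with the totals by sequence tabulated above.

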3.2 Scientific Rationale for Study Design

In [name] clinical experience as Director of the HFpEF Program for the Aging, he has found that some subjects feel better with beta-blockers while others feel worse. This idea is supported by opposing pathophysiologic mechanisms highlighted in the literature—on the one hand, beta-blockers can slow down heart rate, improve left ventricular filling, and thus improve cardiac output and overall functioning. On the other hand, beta-blockers can exacerbate chronotropic incompetence, worsen cardiac output, and reduce exercise tolerance. Beta-blockers are also a common cause of adverse drug reactions and can worsen physical function in some older adults. There is no readily discernable way to determine which subjects will feel better and which will feel worse. Thus, beta-blocker use in HFpEF is a well-suited and clinically relevant model for developing a subject-centered approach to medication optimization.

3.3 Justification for Dose

During the initial “On” [A] period, the target dose will be the one that was prescribed by their usual physician at the time of study enrollment. Justification for the tapering dose is provided above (determined in consultation with other HFpEF experts and pharmacologists; also, this schedule was used in a prior deprescribing study that included beta-blockers).

3.4 End of Study Definition

A subject is considered to have completed the study upon completion of all phases of the study, including the last visit or the last scheduled procedure shown in the **Schedule of Assessments (SoA)**, **Section 6.1**. The end of the study is defined as completion of the last visit or procedure shown in the SoA in the trial.

4. Subject Selection

4.1 Study Population

Subjects with a diagnosis of HFpEF, who are patients at Weill Cornell Medicine, and meet all inclusion and exclusion criteria, will be eligible for participation in this study.

4.2 Inclusion Criteria

1. Ambulatory adults age ≥ 65 years with HFpEF according to ACC/AHA guidelines (signs and symptoms of Heart failure AND ejection fraction $\geq 50\%$)
2. Taking beta-blocker

4.3 Exclusion Criteria

1. Alternate causes of HFpEF Syndrome:
 - a. Severe aortic stenosis and mitral stenosis
 - b. Constrictive pericarditis
 - c. High Output HF
 - d. Infiltrative cardiomyopathy
2. Other compelling indication beta-blocker
 - a. Prior EF $< 50\%$
 - b. Hypertrophic cardiomyopathy
 - c. Angina symptoms
 - d. Acute coronary syndrome, myocardial infarction or coronary artery bypass surgery in prior 3 years
 - e. History of ventricular tachycardia
 - f. Atrial arrhythmia with hospitalization for rapid ventricular response, prior 1 year
 - g. Sinus tachycardia > 100 bpm, atrial arrhythmia with ventricular rate > 90 beats per minute, systolic blood pressure > 160 mmHg
3. Clinical instability (N-of-1 trials are appropriate for stable conditions only)
 - a. Decompensated heart failure
 - b. Hospitalized in past 30 days
 - c. Medication changes or procedures in prior 14 days that could confound observations/data, at PI discretion
4. Estimated life expectancy < 6 months
5. Moderate-severe dementia or psychiatric disorder precluding informed consent
6. Any condition that, in Principal Investigator's opinion, makes the patient unsuitable for study participation

4.4 Lifestyle Considerations

Not applicable.

4.5 Screen Failures

Screen failures are defined as subjects who consent to participate in the clinical trial but are not subsequently randomly assigned to the study intervention or entered in the study. A minimal set of screen failure information is required to ensure transparent reporting of screen failure subjects, to meet the Consolidated Standards of Reporting Trials (CONSORT) publishing requirements and to respond to queries from regulatory authorities. Minimal information includes demography, screen failure details, eligibility criteria, and any serious adverse event (SAE). We are not anticipating any screen failures, as only eligible subjects (based on pre-screening) will be consented. All subjects will be randomized upon gaining consent (no additional screening procedures are necessary).

In the instance of a screen failure, we will not re-screen the subject in the future.

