4.6 Strategies for Recruitment and Retention

Subjects will be recruited primarily from the HFpEF Program at Weill Cornell Medicine. Cardiology, Geriatrics, and Primary Care clinics may be screened in addition if necessary. Approximately 70% of patients seen between July 2018-October 2019 in the HFpEF clinic would be eligible to participate. By 2020 the HFpEF Program will see >200 unique patients, which will provide a sufficient number of subjects to enroll from. We plan to enroll 16 subjects.

The research assistant will screen subjects scheduled in the HFpEF Program in advance of their appointments to identify potentially eligible subjects. The research assistant will then introduce the study to each eligible subject and conduct the informed consent process. A screening and enrollment log will be kept by the research assistant. Subjects will receive \$50 upon consenting, randomization, and completing the baseline assessment. All subjects will provide written informed consent and HIPAA notifications.

We will not enroll the following vulnerable populations:

- Pregnant women
- Children
- Those who lack capacity to consent
- Employee/student volunteers

Planned enrollment is estimated based on frequencies observed in the HFpEF Program at Weill Cornell Medicine. Frequencies in the HFpEF Program are as follows:

- 57% Women
- 62% White non-Hispanic
- 16% Black non-Hispanic
- 11% Hispanic/Latino

Strategies for Retention: There are several opportunities to engage subjects to ensure retention. We will contact subjects weekly to instruct them to complete standardized web-based patient-reported outcomes questionnaires. Subjects will be asked to complete these assessments on their tablet computer (which we will provide free-of-charge and has internet capabilities), over the phone, or via email. We will also conduct routine phone calls for safety purposes (at this time, we can remind subjects to complete the weekly assessments if needed). For subjects who do not complete the assessments (we will track this electronically), we will call them daily to remind them and/or assist them with completing the assessments over the phone. If we are unable to contact the

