6.1.1 Baseline In-Person Visit

- Informed consent
- Randomization
 - Eligible subjects will be randomly assigned to into Arm 1 (ABAB) or Arm 2 (BABA) with a 1:1 ratio using a computer-generated randomization scheme developed by the data manager. Arm 1 will be on an On-Off-On-Off (ABAB) drug scheme, while Arm 2 will be Off-On-Off-On (BABA)
- Demographics
- Medication Inventory
- Baseline beta-blocker use
- Physical Exam, including vital signs
- Central blood pressure assessment via the UScom BP+ device
 - This device measures central and brachial blood pressure and blood pressure waveforms at the heart, as well as in the arm.
- Electrocardiogram
- Blood draw for Troponin & NT-proBNP
- Blood draw for future research
- Six-Minute Walk Test
- Exercise test used to assess aerobic capacity endurance. The distance covered over 6 minutes is used as the outcome by which to compare changes in performance capacity.
- Short Physical Performance Battery
 - Combines the results of gait speed, chair stand and balance tests as a predictive tool for possible disability and can aid in the monitoring of function in older people
 - Gait Speed: assesses the subject's lower extremity function
 - Chair Rise: assesses core strength
 - Balance Test: assess the subject's ability to stand unassisted without the use of a cane or walker
- Qualitative interview on understandability of study purpose and design
- Typology Questionnaire
- Health Literacy Questions
- Number Literacy Questions
- Short Graph Literacy
- EQ5D Visual Analogue Scale
- PROMIS-29
- PROMIS-SF 6A
- PROMIS-Sexual Function
- KCCQ-12
- Decision Making Outcomes Questionnaires
 - Decision Conflict Scale
 - Decision Conflict Subscale
 - Patient Activation Measure (PAM) Survey
 - Shared Decision Making Questionnaire
 - Revised Patient Attitude Towards Deprescribing Questionnaire (rPATD)

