8.2 Subject Discontinuation/Withdrawal from the Study

Subjects are free to withdraw from participation in the study at any time if they wish.

An investigator may discontinue or withdraw a subject from the study for the following reasons:

- Pregnancy
- Significant study intervention non-compliance
- If any clinical adverse event (AE), or other medical condition or situation occurs such that continued participation in the study would not be in the best interest of the subject (this will be decided on conjunction with their own physician and/or the DSMB).
- Disease progression which requires discontinuation of the study intervention
- If the subject meets an exclusion criterion (either newly developed or not previously recognized) that precludes further study participation
- Subject lost to follow-up after several attempts to contact subject to schedule study visit.

The reason for subject discontinuation or withdrawal from the study will be recorded on the Case Report Form (CRF) in REDCap. Subjects who sign the informed consent form and are randomized but do not receive the study intervention may be replaced. Subjects who sign the informed consent form, and are randomized and receive the study intervention, and subsequently withdraw, or are withdrawn or discontinued from the study, will be replaced.

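### Randomisation on consent precedes the baseline visit's measurements for changeable exclusion criteria and its decision questionnaires; it should be the last step of that visit

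*Combined protocol and SAP*

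**What the plan says.** Section 4.5 states "All subjects will be randomized upon gaining consent (no additional screening procedures are necessary". The sentence before it gives the ground for this: "only eligible subjects (based on pre-screening) will be consented". The same section expects no screen failures and does not allow a screen failure to be screened again.

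Section 4.6 describes the pre-screening: "The research assistant will screen subjects scheduled in the HFpEF Program in advance of their appointments to identify potentially eligible subjects". A screening and enrolment log is kept, but no data source or look-back window is given. The same section makes the first payment due "upon consenting, randomization, and completing the baseline assessment".

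Among the exclusions in section 4.3, 2g reads "Sinus tachycardia > 100 bpm, atrial arrhythmia with ventricular rate > 90 beats per minute, systolic blood pressure > 160 mmHg", 2c is angina symptoms and 3a is "Decompensated heart failure".

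Section 6.1.1 lists consent and randomisation near the top of the baseline visit. "Physical Exam, including vital signs", the electrocardiogram, the Short Physical Performance Battery (SPPB) and all questionnaires come below. Section 7.8 says the study is unblinded and that the study team randomises. Section 8.2 includes, among the reasons for which an investigator may withdraw a subject, "If the subject meets an exclusion criterion (either newly developed or not previously recognized) that precludes further study participation".

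**The concern.** Sections 2.3.3 and 4.3 rely on the exclusions to keep out people with another reason to stay on a beta-blocker. Some of those exclusions describe a state that can change between a chart review and the visit. The visit already collects what is needed to confirm them, but the plan assigns the sequence first.

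Two things are at stake. The first is clean accounting: someone who should be recorded as a screen failure enters the trial as a randomised subject, and section 12 does not say how such a subject is handled in the analysis. The second is the quality of one set of baselines. The exploratory endpoints ask what N-of-1 trials do to decision conflict, patient activation, shared decision-making and attitudes to deprescribing. A subject who has just learned whether dose reduction starts now or a period later may answer those questionnaires differently.

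**Working it through.** The point concerns the order of procedures. The plan states no figure to reproduce, so the check sets the sections side by side.

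1. **Order of steps.** Section 4.5 places randomisation upon consent with no screening in between. Section 4.6 names consent, randomisation and baseline assessment in that order. The list in 6.1.1 agrees, though it is not labelled chronological. Section 11.2.3 requires consent before participation, so the research ECG and questionnaires cannot precede it. If randomisation happens upon consent, they follow randomisation.

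2. **Criteria that can change.** Exclusion 2g needs a current heart rate, rhythm and systolic pressure. Exclusions 2c and 3a need current symptoms and clinical state. No section requires any of them to be confirmed at the visit before assignment.

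3. **Status of a subject found ineligible that day.** Section 4.5 defines a screen failure as someone who consents but is not then randomised or entered. Randomising on consent leaves almost nobody who can meet that definition. Under 8.2 the investigator may withdraw the subject. A randomised subject who has not received the intervention may be replaced; replacement is definite only after the intervention has been received. A failure noticed at baseline, before any dose change, most naturally falls in the first group.

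4. **Exposure.** Under section 3.1 both sequences contain an Off period. Arm 1 stays on the home dose in weeks 1-6 and is tapered from week 7; Arm 2 is tapered from week 1. Section 2.3.3 schedules a call on the day before each planned dose change. The baseline findings should therefore be available before the first reduction, and sections 8.1 and 8.2 allow the investigator to act on them.

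5. **Analyses that could use a baseline value.** The On/Off models in 12.4 contain treatment, period, carry-over and a patient random intercept, with no baseline covariate. Step count and patient-reported outcomes are taken from the last two weeks of each period. The exploratory decision endpoints are different: their natural reference is the baseline Decision Conflict Scale, Patient Activation Measure (PAM), shared decision-making questionnaire and revised Patient Attitudes Towards Deprescribing questionnaire (rPATD).

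6. **Size.** One subject is 1/16 = 6.25% of the sample. With 1:1 allocation, 16 × 1/2 = 8 subjects are expected to start Off. If the sequence is disclosed at randomisation, about 8 would complete the baseline decision questionnaires knowing that dose reduction comes first, and about 8 knowing that it comes later.

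**The case against.** The strongest reply is that eligibility is checked before assignment: only pre-screened subjects are consented, and 6.1.1 speaks of randomising eligible subjects. That stands, and it narrows the gap to criteria that can change after pre-screening. Clinic vital signs might in practice feed the pre-screening, but the documents do not say so.

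A reader might infer that ineligible subjects will be exposed to withdrawal before anyone notices. The documents do not support that. Randomisation decides only the order of On and Off, and the baseline findings can be acted on before the first dose change (steps 3 and 4 above). Nor is such a subject automatically replaced.

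A reader might also infer that the patient-reported and SPPB comparisons are biased by an unblinded baseline. They are not, because the On/Off models use no baseline value.

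The moment at which the subject learns the sequence is not stated. Disclosure before the questionnaires is an inference from the open-label design and the absence of any rule withholding it. All subjects have also already agreed to a trial with both On and Off periods, so knowing the order may add little. The direction and size of any effect on the answers are unknown. These limits stand.

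**Conclusion.** The order of steps is a real weakness with limited consequences. Subjects are randomised before changeable exclusions are confirmed at the visit, so a same-day failure becomes a possible post-randomisation withdrawal. The baseline decision questionnaires may be completed with the sequence known, which touches exploratory endpoints only.

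It is tempting to attach a probability. Assumed same-day failure rates of 5% or 10% would give 1 - 0.95^16 = 56% or 1 - 0.90^16 = 81% for at least one such subject among 16. Neither rate has any basis in the documents, so these figures are no evidence that the problem is common. What can be said is that each occurrence costs 6.25% of a small sample.

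The conclusion assumes that section 4.5 is followed as written and, for the questionnaires, that the sequence is disclosed when it is assigned. It is worth correcting mainly because the correction is so cheap.

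**What to change.** In sections 4.5 and 6.1.1, make randomisation and disclosure of the sequence the last step of the baseline visit. It should follow a documented check of that day's vital signs, physical exam and ECG against the existing section 4.3 criteria, and completion of all baseline questionnaires. Delete the parenthesis in 4.5 that says no further screening is needed, and revise the expectation of no screen failures. Align the order of steps in 4.6.

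This adds no procedure, changes no eligibility threshold and needs no change in sample size. The cost is a few recorded screen failures, which 4.5 already provides for. Because 4.5 bars re-screening, a subject who fails on a single reading that day could not return. The bar and the new order must therefore be reconciled; how to do so is for the investigators to decide.
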